The primary endpoint of this study, ORR, is based on tumor assessments at baseline and then at 6 weeks from first dose. Tumor assessments continue every 6 weeks for the first 24 weeks and every 12 weeks thereafter while on treatment or on treatment hold for any reason until disease progression (investigator-assessed RECIST 1.1-defined progression) or treatment discontinuation, except for subjects treated beyond progression or who discontinued treatment for other reasons than PD.

Statistical Considerations:

Sample Size Determination

Sample size determination in the original protocol

This study comprises a Dose Escalating Safety Evaluation Phase for the Combination Arm, followed by a Staged Enrollment for Arm N, and Arm N-I.

In the original protocol, gastric cancer, small cell lung cancer, triple negative breast cancer, and pancreatic cancer are included and the Staged Enrollment Part utilizes a modified Simon two-stage design with the treatment of 40 subjects to evaluate whether nivolumab, or the combination of nivolumab/ipilimumab yields an objective response rate (ORR) that is of clinical interest. In this study, an ORR of 10% or less is considered not of clinical value, and an ORR of 25% or greater is considered of strong clinical interest. The modified Simon design evaluates the null hypothesis that the true response rate is $\leq 10\%$ versus the alternative hypothesis that the true response rate is $> 10\%$. The 2-stage testing within each cohort targets a Type I error rate of 5% and has 80% power to reject the null hypothesis if the true response rate is 25%.

Sample size determination for bladder cancer cohort

In Amendment 06, the bladder cohort is added. A one stage design with the treatment of 60-100 subjects is used for nivolumab monotherapy and the dose level 2b. These sample sizes will provide 90% to 97% power to reject the null hypothesis of 10% response rate if the true response rate is 25% with a two-sided Type I error rate of 5%.

In Amendment 14, the dose level 2 arm (nivolumab 1 mg/kg + ipilimumab 3 mg/kg) of the bladder cancer cohort is to enroll and treat a total of 92 subjects. A one stage design will be used. Based on a 19.6% ORR for nivolumab monotherapy (CA209275), the sample size of 92 in this arm will provide 93% power to reject the null hypothesis of 19.6% response rate if the true response rate is 35% with a two-sided Type I error rate of 5%.

Sample size determination for SCLC expansion cohort

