3.1.3 Staged Enrollment (Stage 1 and Stage 2)

3.1.3.1 Stage 1

This Stage is intended to assess the efficacy in 18 subjects per treatment arm per tumor type to determine whether enrollment should continue to Stage 2. For efficacy determination, each Arm within each tumor type will be assessed independently.

Arm N: The enrollment and treatment of 18 subjects to Arm N per tumor type can begin while the initial Dose Cohort for Arm N-I in this tumor type is still ongoing. The dose level in Arm N is 3 mg/kg nivolumab IV every two weeks (Q2W). This dose has been established in more than 700 subjects with various tumor types exposed to nivolumab monotherapy with a tolerable AE profile. Therefore no dose adjustments for Arm N are planned.

Arm N-I: Up to 18 subjects will be enrolled and treated in this arm per tumor type at the highest tolerated Dose Level determined during the Dose Escalating Safety Evaluation phase. The 3-9 subjects treated at the highest dose level confirmed for further investigation from the Dose Escalating Safety Evaluation phase will be counted as part of the 18 required subjects.

3.1.3.2 Criteria to proceed from Stage 1 to Stage 2

The decision to proceed from Stage 1 to Stage 2 will be made for each tumor and for each treatment arm independently and include ([Table 3.1.3.2-1](#)):

- 2 or more of 18 subjects in a given arm must have confirmed PR or CR before enrollment for that arm will be continued in Stage 2. The tolerability of the regimen will continue to be evaluated by the Sponsor with the investigators to ensure that it is acceptable for continued enrollment.
 - Subjects with initial PD per RECIST 1.1 who continue treatment in their initially assigned treatment arm beyond progression ([Section 4.5.7](#)) and subsequently reach confirmed immune related CR or PR (relative to initial tumor assessment) and including any new measurable lesions within the sum of all target lesions, will be considered as having an objective response for the purposes of meeting criteria for moving from Stage 1 to Stage 2. Although not standard RECIST 1.1, these immune related response criteria using unidimensional measurements account for the unusual immune related tumor response patterns reported for both ipilimumab and nivolumab.

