- Once the last subject in a given treatment arm has permanently discontinued treatment for any reason or has reached the Week 48 Tumor Assessment, and the above criteria are not met, then this treatment arm will not proceed to Stage 2. Ongoing subjects will continue to be followed up for efficacy and safety.
- In case that 2 or more of subjects in a given arm enrolling in Stage 1 have confirmed PR or CR, but the enrollment of 18 subjects for Stage 1 has not been completed or 18 subjects have been enrolled but have not been randomized and started treatment at that timepoint, the following applies:
 - Arm N: the enrollment for that arm can be continued in Stage 2. The tolerability of the regimen will continue to be evaluated by the Sponsor with the investigators to ensure that it is acceptable for continued enrollment.
 - Arm N-I: at least 9 subjects need to have been exposed to the highest dose level which has been confirmed for Stage 1 and followed up for at least 6 weeks after start of study treatment before the enrollment for that arm can be continued in Stage 2. The tolerability of the regimen will continue to be evaluated by the Sponsor with the investigators to ensure that it is acceptable for continued enrollment.

Table 3.1.3.2-1: Efficacy criteria to proceed from Stage 1 to Stage 2

Efficacy criteria	Next Step
2 or more of 18* subjects in a given arm have confirmed PR or CR	Go into Stage 2
1 or no of 18* subjects in a given arm have confirmed PR or CR.	No Go into Stage 2

* see [Section 3.1.3.2](#) last bullet point for further clarification

3.1.3.3 Stage 2

Arm N: For treatment **Arm N** of the given tumor type that continues to Stage 2, additional subjects will be assigned to a total of 40 subjects, inclusive of those enrolled in Stage 1. For tumor types where nivolumab monotherapy proceeded to Stage 2, assessment of Dose Level 2b in Stage 2 (nivolumab 3 mg/kg + ipilimumab 1 mg/kg, n=40 subjects) will be initiated for that tumor type. A separate evaluation of Dose Level 2b may be necessary if the safety and tolerability of Dose Level 2 has not been confirmed.

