- Treated subjects will be evaluated for response according to the RECIST 1.1 guidelines beginning 6 weeks (± 1 week) after first dose and continuing every 6 weeks (± 1 week) for the first 24 weeks, and then every 12 weeks (± 1 week) while on treatment or on treatment hold for any reason until disease progression (investigator-assessed RECIST 1.1-defined progression) or treatment discontinuation, except for subjects treated beyond progression or who discontinued treatment for other reasons than PD.

This phase ends when the subject is discontinued from study therapy. For a complete list of reasons for treatment discontinuation, see [Section 4.5.5](#).

Follow-Up Phase

- Begins when the decision to discontinue a subject from study therapy is made (no further treatment with study therapy).

Two follow-up visits include collection of PK/immunogenicity samples [Table 5.1-7](#), [Table 5.5.1-1](#), and [Table 5.5.1-2](#).

- Subjects who discontinue treatment for reasons other than tumor progression will continue to have tumor assessments beginning 6 weeks (± 1 week) after first dose and continuing every 6 weeks (± 1 week) for the first 24 weeks from first dose, and every 12 weeks (± 1 week) thereafter until disease progression (investigator-assessed RECIST 1.1-defined progression).

This does also apply to subjects whose treatment was put on hold after achieving confirmed CR or PR for more than 3 month (long lasting PR).

- Subjects will be followed for drug-related toxicities until these toxicities resolve, return to baseline or are deemed irreversible. All adverse events will be documented for a minimum of 100 days after last dose.
- Follow up visits should be made in-person. If a subject is unable to make an in-person visit, the reason should be clearly documented at the site.
- Follow-up visit 1 (FU1) = 35 days from the last dose \pm 7 days or coincide with the date of discontinuation (\pm 7 days) if date of discontinuation is greater than 42 days after last dose, Follow-up visit 2 (FU2) = 80 days (\pm 7 days) from follow-up visit 1.
- After completion of the first two follow-up visits, subjects will be followed every 3 months for survival via in-person visits, phone or email. Ad hoc survival data requests may be made during the study as well, particularly during database locks.

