3.6 Post Treatment Study Follow up

In this study, objective response rate is a key endpoint of the study. Tumor responses initiated by immunotherapy with nivolumab, nivolumab combined with ipilimumab, or nivolumab combined with ipilimumab and cobimetinib may evolve after treatment discontinuation. Therefore, post treatment study follow-up is of critical importance and is essential to preserving subject safety and the integrity of the study. Subjects who discontinue study treatment must continue to be followed for collection of outcome and/or survival follow-up data as required and in line with [Section 5](#) until death or the conclusion of the study.

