5.4.2 Best Overall Response

The best overall response is determined once all the data for the subject is known. It is defined as the best response designation, as determined by the investigator or BICR for selected tumor types, recorded between the date of first treatment and the date of objectively documented progression per RECIST1.1 or the date of subsequent therapy, whichever occurs first. For subjects without documented progression or subsequent therapy, all available response designations will contribute to the BOR assessment. The subject's best overall response assignment will depend on the findings of both target and non-target disease and will also take into consideration the appearance of new lesions.

Complete or partial responses may be claimed only if the criteria for each are met at a subsequent time point (minimum 4 weeks after criteria of objective response are first met). In this circumstance, the best overall response can be interpreted as in Table 5.4.2-1.

Table 5.4.2-1: Best overall response when confirmation of CR and PR required

Overall Response First Timepoint	Overall Response Subsequent Timepoint	Best Overall response
CR	CR	CR
CR	PR	SD, PD or PR ^a
CR	SD	SD provided minimum criteria for SD duration met, otherwise, PD
CR	PD	SD provided minimum criteria for SD duration met, otherwise, PD
CR	NE	SD provided minimum criteria for SD duration met,

Table 5.4.2-1: Best overall response when confirmation of CR and PR required

Overall Response First Timepoint	Overall Response Subsequent Timepoint	Best Overall response
		otherwise NE
PR	CR	PR
PR	PR	PR
PR	SD	SD
PR	PD	SD provided minimum criteria for SD duration met, otherwise, PD
PR	NE	SD provided minimum criteria for SD duration met, otherwise NE
NE	NE	NE

CR = complete response, PR = partial response, SD = stable disease, PD = progressive disease, and NE = inevaluable.

^a If a CR is truly met at first time point, then any disease seen at a subsequent time point, even disease meeting PR criteria relative to baseline, makes the disease PD at that point (since disease must have reappeared after CR). Best response would depend on whether minimum duration for SD was met. However, sometimes ‘CR’ may be claimed when subsequent scans suggest small lesions were likely still present and in fact the patient had PR, not CR at the first time point. Under these circumstances, the original CR should be changed to PR and the best response is PR.

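### The Stage 1 No-Go rule can close an arm while a deciding response is still awaiting its confirming scan; the effect is modest and one added sentence repairs it

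*Protocol*

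**What the plan says.** Section 3.1.3.2 sets the Go criterion: "2 or more of 18 subjects in a given arm must have confirmed PR or CR". A confirmed immune-related CR or PR also counts when it follows RECIST progression in a subject treated beyond progression in the assigned arm.

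The same section sets the No-Go trigger: "Once the last subject in a given treatment arm has permanently discontinued treatment for any reason or has reached the Week 48 Tumor Assessment". If the criterion is unmet at that point, "then this treatment arm will not proceed to Stage 2. Ongoing subjects will continue to be followed up for efficacy and safety". It states no way to reopen the decision. Both protocol versions in the file (Revised Protocol 07d and 08) carry this wording.

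Three other provisions bear on the rule:

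- **Confirmation, section 5.4.2:** "Complete or partial responses may be claimed only if the criteria for each are met at a subsequent time point", with a "minimum 4 weeks after criteria of objective response are first met".
- **Scan schedule, synopsis:** "Tumor assessments continue every 6 weeks for the first 24 weeks and every 12 weeks thereafter while on treatment". Section 3.1.12 adds: "Subjects who discontinue treatment for reasons other than tumor progression will continue to have tumor assessments".
- **Late responses, section 3.6:** responses "may evolve after treatment discontinuation. Therefore, post treatment study follow-up is of critical importance".

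**The concern.** What is counted and when counting stops are tied to different things. Go depends on confirmed response, which always lags the first response scan by at least 4 weeks. No-Go depends on treatment status or a calendar visit, with no allowance for that lag.

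An arm with one confirmed response and a second awaiting its confirming scan can therefore be closed as written, even though the confirming scan is already on the schedule. The error runs in one direction: an active arm may be dropped. The protocol recognises elsewhere that subjects who stop treatment may be responders. Section 3.6 says so directly, and section 3.1.2.1 provides for the case where most subjects who discontinue for toxicity have deep tumor responses.

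**Working it through.** **1. Timing.** Scheduled scans fall at Weeks 6, 12, 18, 24, 36, 48 and 60, each ± 1 week.

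- *Discontinuation leg.* Suppose the last subject on treatment has a first PR at Week 6 and stops permanently for toxicity in Week 7. The trigger fires in Week 7, while section 3.1.12 already schedules the confirming scan for Week 12.
- *Week 48 leg.* A response first seen by Week 36 can be confirmed at Week 48. One first seen at Week 48 is confirmed on schedule only at Week 60. This leg loses only responses first seen at Week 48 or later.

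The discontinuation leg is therefore the weaker of the two.

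**2. The plan's own figure.** Section 8.1 gives 40 subjects, a null ORR of 10%, an alternative of 25%, a 5% type I error target and 80% power. The final cut-off is not stated. With X₁ ~ Bin(18, p) and X₂ ~ Bin(22, p), the success probability is

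Σ over x ≥ 2 of P(X₁ = x) · P(X₂ ≥ r − x).

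| Final cut-off r (of 40) | Type I error (p = 0.10) | Power (p = 0.25) |
|---|---|---|
| 7 | 9.3% | 88.6% |
| 8 | 4.05% | 80.7% |
| 9 | 1.5% | 69.4% |

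Only r = 8 meets both stated targets, so it is used below as an assumption. The plan's figures reproduce, on the premise that every Stage 1 responder is counted at the gate.

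**3. False No-Go with full ascertainment.** At p = 0.25:

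P(X₁ ≤ 1) = 0.75¹⁸ + 18 · 0.25 · 0.75¹⁷ = 0.0056 + 0.0338 = 0.0395, quoted as 3.9% (0.03946 unrounded).

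**4. False No-Go when responses may be pending.** The protocol gives no rate for this. Assume that in the last k subjects a true response has a 20% chance of being unconfirmed at the trigger. Those k subjects then count as responders with probability 0.25 × 0.80 = 0.20, and the other 18 − k with 0.25. For k = 1:

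0.75¹⁷ · 0.80 + 17 · 0.25 · 0.75¹⁶ · 0.80 + 0.75¹⁷ · 0.20 = 0.0060 + 0.0341 + 0.0015 = 0.0416.

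The other rows use the same sum. Power applies the gate to confirmed responders and counts all true responders at the end, with r = 8.

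| Subjects at risk of a pending response | False No-Go at ORR 25% | Power |
|---|---|---|
| none | 3.9% | 80.7% |
| last 1 | 4.2% | 80.6% |
| last 3 | 4.6% | 80.4% |
| last 6 | 5.4% | 80.0% |
| all 18 (extreme) | 9.9% | 77.2% |

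If the last subject's response were always lost, the figure would be P(≤ 1 of 17) = 0.75¹⁷ + 17 · 0.25 · 0.75¹⁶ = 0.0075 + 0.0426 = 5.0%.

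**5. Type I error.** A stricter gate cannot raise it. At ORR 10% it falls from 4.05% to 3.7% in the extreme row.

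**The case against.** The strongest reply is that the trigger belongs to the arm, not to each subject. It waits for the slowest of 18, and section 3.1.3.2 does not require a response to be confirmed on treatment. A subject who stops early, keeps being scanned and is confirmed before that date counts. A reader might infer that the rule disregards off-treatment responses altogether, or that 10% to 20% of all responders are lost, giving a false No-Go of 6.3% to 9.9%. The documents do not support either reading. The second treats all 18 subjects as if each were cut off at their own discontinuation.

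Nor does the 18.9% (10 of 53) who stopped combination treatment for related adverse events in CA209004 (section 1.1.8.2) measure pending responses. It covers all combination subjects pooled over dose cohorts, including one above the maximum tolerated dose.

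Other limits also stand:

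- The decision changes only if fewer than 2 responses are confirmed at the trigger and pending ones would make up the number.
- Section 1.1.9 says most combination responses in CA209004 came in the first 12 weeks.
- Dose delays, and treatment holds for lasting responders, are not permanent discontinuation.
- Reach is narrow: both SCLC arms have already passed the gate (section 3.1.4), and the bladder, ovarian and additional pancreatic cohorts are one-stage.
- Any finite cut-off misses some late responses.

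These points reduce the size of the problem. They do not supply the missing allowance: section 3.1.8 has the decision made with the investigators, but gives no exception to the categorical closure.

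**Conclusion.** The concern holds in a limited form. As written, the rule can close a two-stage arm with a deciding CR or PR already observed and its confirming scan already scheduled. That sits badly with sections 3.1.12 and 3.6.

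The cost is a modest rise in false No-Go at a true ORR of 25%, from 3.9% to about 4.2% to 5.4%, with 9.9% as the outer bound. Over the 4.2% to 5.4% range, power stays at about 80%. These figures rest on two assumptions the protocol does not supply: the 20% chance of a pending response with 1 to 6 subjects at risk, and, for power and type I error, the cut-off of 8 of 40. There is no type I error inflation, and nothing here questions the 2-of-18 threshold itself.

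**What to change.** Keep the existing trigger and add one sentence to section 3.1.3.2:

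> If, at that time, any Stage 1 subject has an unconfirmed CR/PR (or irCR/irPR) that could bring the arm to 2 responses, the No-Go decision is deferred until that subject's next scheduled tumor assessment at least 4 weeks after the first response, on or off treatment, or until progression, death or subsequent anti-cancer therapy makes confirmation impossible.

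The trigger should not be replaced by one that treats a subject as resolved at RECIST progression. That would contradict the provision in the same section that counts confirmed immune-related responses after progression, whereas the present trigger keeps such subjects open while they are treated.

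The cost is an occasional No-Go delayed by at most one scan interval, 6 or 12 weeks. No extra scans are needed for a RECIST CR/PR, because section 3.1.12 already schedules them. One detail to settle is that section 3.1.12 provides post-treatment scans only for subjects who stop for reasons other than progression. For an immune-related response pending when treatment beyond progression stops, the text should say whether a confirming scan is expected or the response is taken as unconfirmed.

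The sentence does not rescue responses that first appear after the trigger; some cut-off is needed. For any arm already closed under this rule, check that no response was pending on the closing date.

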3.1.3.4 Modified Design Bladder Cancer Cohort

Bladder arms N and N-I (Dose Levels 2 and 2b) will be conducted as a One Stage Design with the treatment of 26-105 subjects in each arm. The Safety Evaluation Phase for the N-I arm will start at Dose Level 2 (nivolumab 1 mg/kg, ipilimumab 3 mg/kg) and will evaluate safety and tolerability after the first 6 randomized subjects. Following the N-I safety evaluation phase, Dose Levels 2 will treat approximately 92 subjects and 2b will treat up to a total of 105 subjects. Based on the safety evaluations thus far on study, no dose escalation phase is necessary for bladder cohort N I Dose Level 2b (nivolumab 3 mg/kg, ipilimumab 1 mg/kg).

3.1.3.5 Arm N-I (Dose Level 2b)

Based on the safety evaluations thus far on study, no dose escalation phase is necessary for bladder cohort N-I Dose Level 2b (nivolumab 3 mg/kg, ipilimumab 1 mg/kg).

3.1.4 SCLC Expansion

SCLC cohorts Arm N and Arm N-I met the pre-specified safety and efficacy criteria and proceeded to Stage 2. Based on an interim data review, disease control rates (SD + PR + CR) of 36% and 57% for Arms N and N-I, respectively, were estimated. In order to further investigate nivolumab and nivolumab combined with ipilimumab activity in specific SCLC subpopulations, the SCLC expansion cohorts will enroll additional subjects based on response to prior treatment and the number of previous therapies. Up to 250 second or third line subjects will be randomized in a 3:2 ratio to one of 2 expansion groups: Arm A (150 subjects treated with nivolumab 3 mg/kg every 2 weeks (Q2W)) or Arm B (100 subjects treated with nivolumab 1 mg/kg + ipilimumab 3 mg/kg every 3 weeks (Q3W) for 4 cycles followed by nivolumab 3 mg/kg (Q2W) and will be stratified for number of prior treatment lines (1 vs 2 prior chemotherapy regimens).

The study population for the SCLC expansion cohort is specified as follows:

- Histopathologically or cytologically confirmed diagnosis of SCLC.
- All subjects had platinum-based first-line treatment. Subjects with previous second-line chemotherapy treatment are eligible as well.
- Subjects with platinum refractory, resistant, or sensitive disease are eligible.
- Subjects with initial diagnosis of limited or extensive disease are eligible.
- Documented objective radiographic disease progression at study entry.

Tumor assessments for subjects in the SCLC expansion cohort will undergo a BICR assessment. The crossover option refers only to the original cohorts and not the new cohorts enrolled under or after Amendment 09.

3.1.5 Duration of Study Treatment

The study treatment will be continued until disease progression (investigator-assessed RECIST 1.1-defined progression) or occurrence of unacceptable toxicity as defined in [Section 4.5.5](#). For subjects achieving confirmed CR or a PR for more than 3 months (long lasting PR) the investigator may decide to hold treatment for this subject after discussion with the medical monitor of the sponsor. During the treatment hold subjects should follow all study procedures as specified in [Section 5.1](#). Subjects for which treatment was held following long lasting responses and who experience a recurrence of disease progression may reinitiate their last study treatment. Before reinitiating treatment, the investigator should discuss the individual case with the medical monitor and document in the study records.

